2.2 Per-Protocol Population

The PP population is defined as a subset of the ITT population excluding major protocol violators. The following is a list of some of the conditions which, if met, would likely exclude the patient from the PP population:

- Violation of inclusion or exclusion criteria
- Breaking the blind
- Randomization irregularities
- Withdrawal from the study before week 12
- Current use of prohibited DMARDs or biological RA treatments per protocol
- Any other relevant violations observed during the conduct of the trial

Final specification of the criteria, definitions and processes are detailed in the 'Blinded Review Report of Deviations Leading to Exclusion from the Per-Protocol Analysis' document.

Patients will be analyzed based on the treatment received. Analyses on the PP population will be seen as supportive analyses. The primary and secondary efficacy endpoints will be analyzed for the PP population.

The list of protocol deviations leading to exclusion from the PP population will be finalized before database lock. During the blind data review before database lock the PP population will be defined by determining subjects not eligible for the PP population and the reason they cannot be included.

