2.4 Safety Population

The safety population (SAF) will include all patients who receive at least one infusion or part of infusion with Nanocort/placebo or at least one IM injection or

part of IM injection with Depo-Medrol/placebo and had at least one post baseline safety assessment.

Patients will be assigned to treatment groups as treated for analysis.

3. Blinded Review of the Data

A blinded data review will be held before breaking the blind. The blinded data review will be performed by at least the Principal Investigator, the Medical Monitor, the Study Lead and the Trial Statistician. The goal of the blinded data review is to determine for each subject the maintenance of improvement at 12 Weeks, the protocol violations and to evaluate the impact of these protocol violations on the EULAR response.

The decisions taken during the blinded data review will be finalized and signed by participants on the blinded data review report before unblinding.

4. Statistical and Analytical Methods

This analysis plan gives a detailed description of the statistical methodologies, data listings, and summary tables planned in the analysis of the data in the CLR-15-05 study. This section describes the statistical analyses of the study based on the statistical section of the protocol (CLR15_05_Prot_V3.1_Amend_25Sep2017.pdf). Any difference with the protocol will be identified and documented. The statistical data analysis, described in this document, is intended to provide unbiased and valid conclusions concerning the objectives of the study.

This SAP describes only the analyses for the study objectives not involving the PK objectives. The PK objectives will be described in a separate analysis plan.

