Listing 2	Subjects Excluded from the Analysis Populations (randomized subjects)
Listing 3	Protocol Violations (SAF)
Listing 4	Visit Windows (SAF)
Listing 5	Demographics and Baseline Characteristics (SAF)
Listing 6.A	Medical and Surgical History (SAF)
Listing 6.B	Medical and Surgical History with MedDRA Coding (SAF)
Listing 7.A	Dosing Administration (SAF)
Listing 7.B	Dosing Administration (cont'd) (SAF)
Listing 7.C	Doses Not Given According to Protocol – Interrupted (SAF)
Listing 7.D	Doses Not Given According to Protocol – Discontinued (SAF)
Listing 7.E	Doses Not Given According to Protocol – Adjusted Rate (SAF)
Listing 8	DAS28 Scores and EULAR Response (SAF)
Listing 9	Swollen and Tender Joints (SAF)
Listing 10.A	Visual Analog Scale (VAS) – Patient Assessment of General Health and Pain (SAF)
Listing 10.B	Visual Analog Scale (VAS) – Patient and Investigator Assessment of RA Disease Activity (SAF)

CLR_15_05 SAP

Listing 11	American College of Rheumatology (ACR) 20/50/70 Response (SAF)
Listing 12.A	SF-36 Physical and Mental Component Scores (SAF)
Listing 12.B	SF-36 Physical Functioning (SAF)
Listing 12.C	SF-36 Role Limitations Due to Physical Health (SAF)
Listing 12.D	SF-36 Role Limitations Due to Emotional Health (SAF)
Listing 12.E	SF-36 Social Functioning and Pain
Listing 12.F	SF-36 Energy/Fatigue
Listing 12.G	Emotional Well-Being
Listing 12.H	General Health
Listing 13.A	Health Assessment Questionnaire (HAQ) (SAF)
Listing 13.B	Health Assessment Questionnaire (HAQ) (cont'd) (SAF)
Listing 13.C	Health Assessment Questionnaire (HAQ) (cont'd) (SAF)
Listing 13.D	Health Assessment Questionnaire (HAQ) (cont'd) (SAF)
Listing 13.E	HAQ Scores (SAF)
Listing 14	Functional Assessment of Chronic Illness Therapy (FACIT) Fatigue Scale (SAF)
Listing 15.A	Health Economics Questionnaire (HEQ) – Use of Hospital Services (SAF)
Listing 15.B	HEQ – Use of Hospital Services (cont'd) (SAF)
Listing 15.C	HEQ – Use of Hospital Services (cont'd) (SAF)
Listing 15.D	HEQ – Use of Ambulatory Care Services (SAF)
Listing 15.E	HEQ – Use of Ambulatory Care Services (cont'd) (SAF)
Listing 15.F	HEQ – Other Expenses (SAF)
Listing 15.G	HEQ – Other Expenses (cont'd) (SAF)
Listing 16.A	Laboratory – Chemistry (SAF)
Listing 16.B	Laboratory – Hematology (SAF)
Listing 16.C	Laboratory – Urinalysis (SAF)
Listing 16.D	Laboratory – ESR (SAF)
Listing 17	Vital Signs (SAF)
Listing 18	Physical Exam (SAF)
Listing 19	12-Lead ECG (SAF)
Listing 20	Concomitant Medications (SAF)
Listing 21.A	Adverse Events (SAF)

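### Per-protocol membership is set at a blinded review that also examines EULAR response, so exclusions could depend on the primary outcome

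*Combined protocol and SAP*

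**What the plan says.** SAP 3 (Blinded Review of the Data) describes one review, held by at least the principal investigator, the medical monitor, the study lead and the trial statistician. It begins: "The goal of the blinded data review is to determine for each subject the maintenance of improvement at 12 Weeks". The same sentence adds the identification of protocol violations and then a further aim, "to evaluate the impact of these protocol violations on the EULAR response". EULAR response at Day 8 is the primary endpoint (SAP 1.4.1). The decisions "will be finalized and signed by participants on the blinded data review report before unblinding".

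SAP 2.2 places the PP decision at this review: "During the blind data review before database lock the PP population will be defined by determining subjects not eligible for the PP population". The criteria are introduced with "The following is a list of some of the conditions which, if met, would likely exclude the patient from the PP population" and end with "Any other relevant violations observed during the conduct of the trial". Final criteria and processes are left to a separate blinded review report.

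On the role of the analysis, SAP 2.2 states: "Analyses on the PP population will be seen as supportive analyses". SAP 2 names ITT as the primary efficacy population and asks the PP analysis of the primary and key secondary endpoints to confirm the ITT findings.

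**The concern.** A PP population is credible when membership follows from what happened to the subject's treatment and conduct, not from the result. Here the people who decide membership must also judge efficacy subject by subject, are asked to consider violations in relation to the primary variable, and work from criteria that are not closed. No sentence withholds DAS28, EULAR response, joint counts or VAS while membership is settled. A debatable violation could then be called relevant in a non-responder and unimportant in a responder, without anyone intending it.

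Masking the arm is a real safeguard, but against a different problem. It stops reviewers from choosing exclusions by known treatment. It does not stop them from choosing by outcome. If debatable violations are equally common in all arms, such selection raises every PP response rate but leaves the difference unbiased under the null. If they are more common in one arm, selection acts more strongly there and the difference moves. What is at stake is the PP analysis as a check on ITT: a check whose membership may depend on the outcome is weaker confirmation than it appears.

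**Working it through.** The plan states no figure for this point, so there is none to reproduce. The question is how far outcome-dependent exclusion could move the PP difference.

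**Inputs from the documents**
- Planned size: 110 per arm with about 10% drop-out (protocol 4.4), so 110 × 0.90 = 99 evaluable.
- Actual size: not given, but stated to be much smaller than planned (SAP 4.1).
- Infusion reactions: about 9.7% of patients in earlier Nanocort studies (protocol 6.3) and about 5-10% for liposomes generally (protocol 6.4.1). These are reaction rates, not deviation rates. No rate is given for the saline infusion.
- Dosing listings: SAP 7, Listings 7.C-7.E, cover interrupted, discontinued and rate-adjusted doses under the label "Doses Not Given According to Protocol".

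**Assumed inputs**
- True response rate p, the same in all arms (no effect): 0.3 to 0.7.
- Share d of subjects with a debatable deviation, unrelated to response.
- Share e of non-responding deviators who are excluded; every responding deviator is kept. The worst case is e = 1.

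**Formula.** Responders stay at p and non-responders shrink to (1−p)(1−d·e), so

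PP rate = p / [1 − d·e·(1−p)].

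**Worked case.** With p = 0.5 and e = 1, d = 12% on Nanocort gives 0.5/0.940 = 53.19%, and d = 1% on control gives 0.5/0.995 = 50.25%. The shift is +2.94 points.

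| Deviation rate, Nanocort vs control | p | e | Shift in PP difference (points) |
|---|---|---|---|
| 12% vs 1% | 0.5 | 1 | +2.94 |
| 12% vs 1% | 0.5 | 0.5 | +1.42 |
| 5% vs 1% | 0.5 | 1 | +1.03 |
| 5% vs 1% | 0.5 | 0.5 | +0.51 |
| 5% vs 0% | 0.3 / 0.5 / 0.7 | 1 | +1.09 / +1.28 / +1.07 |
| 9.7% vs 0% | 0.3 / 0.5 / 0.7 | 1 | +2.19 / +2.55 / +2.10 |
| 9.7% vs 3% | 0.3 / 0.5 / 0.7 | 1 | +1.54 / +1.79 / +1.46 |
| 9.7% vs 9.7% | 0.3 / 0.5 / 0.7 | 1 | 0 / 0 / 0 |

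In the equal-rate row at p = 0.5, both arms rise to 0.5/0.9515 = 52.5%. The rates are inflated but the difference is not.

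**Type I error** (normal approximation, two-sided 0.05, one comparison). For 9.7% vs 0% and p = 0.5 at 99 per arm, the retained numbers are 99 × 0.9515 = 94.2 and 99. The standard error is √(0.5255×0.4745/94.2 + 0.25/99) = 0.0719, and 0.0255/0.0719 = 0.35. The error is then Φ(−1.96+0.35) + Φ(−1.96−0.35) ≈ 0.065. Over p = 0.3 to 0.7 it is 0.062-0.065 at 99 per arm and about 0.054 at an assumed 30 per arm. For 9.7% vs 3% it is 0.056-0.057 at 99 per arm. With equal rates it is 0.050.

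**Direction.** If reviewers instead dropped every responding deviator and kept the non-responders, the sign would reverse. At p = 0.5 and d = 9.7% vs 0%, the Nanocort rate is 0.5×0.903/0.9515 = 47.45%, a shift of −2.55 points.

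**Small numbers.** At an assumed 30 per arm with 15 responders, excluding two non-responders moves that arm from 15/30 = 50.0% to 15/28 = 53.6%.

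**The case against.** The strongest case against has four parts.

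First, a reader might infer from SAP 3 that every violation is weighed against whether that subject responded. The text does not say so. It can equally mean judging whether a kind of violation is capable of affecting the endpoint, which is an ordinary way to separate major from minor. This stands: dependence on outcome is permitted, not prescribed. But the milder meaning is not written down, and maintenance of improvement has to be judged per subject at the same review, so subject-level efficacy information will be needed there.

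Second, a reader might infer that infusion deviations concentrate in the Nanocort arms and that bias in Nanocort's favour follows. The documents do not support that. Every arm receives an infusion (protocol 5.1.3). Protocol 5.1 and 6.6 allow the rate to be changed or the infusion paused for a reaction. No infusion item is a named PP exclusion. The SAP 7 dosing listings are safety listings with no stated link to PP membership. The protocol Summary also says that slower infusion has lowered reaction incidence and that this trial is slower still. What remains is a possibility: liposomal infusions carry a reported reaction rate, the control infusion is saline, and the catch-all could take in altered doses.

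Third, the final criteria may be closed in the blinded review report (SAP 2.2) or the data review plan (protocol 10.8), neither of which is visible here. The exclusion list must be final before database lock. This is fair, but the SAP itself neither closes the list nor withholds outcomes.

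Fourth, PP is supportive and success is judged on ITT (SAP 2.1). This stands and limits the consequence.

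**Conclusion.** The procedural gap is real. The SAP allows PP membership to be decided with knowledge of the primary outcome, under open criteria, at a review that also examines efficacy. That conclusion rests on the text alone and does not depend on any assumed rate.

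Bias in the treatment difference is conditional. Under no true effect it requires deviation rates that differ by arm, which the documents do not establish, and exclusions that depend on response. In the assumed worst case the shift is about +1 to +3 points for rates of 5-12% against 0-1%, roughly half that if only half of the non-responding deviators are dropped, and zero for equal rates. The 12% and 1% inputs are assumptions, and 12% lies above the reported reaction rates. The direction is not fixed either, since masked reviewers could also exclude responders.

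The effect is confined to the supportive PP analysis. The ITT result is untouched. The change is worth making because the PP analysis is given the task of confirming ITT and because, in a trial that stopped well short of plan, a few individual decisions can visibly move a PP response rate.

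**What to change.** In SAP 3, remove the evaluation of EULAR impact as an input to PP membership. State that exclusions are decided from the type, timing and severity of the deviation, using listings that omit DAS28, EULAR response, joint counts and VAS. Require the PP list to be signed before maintenance of improvement or any other efficacy listing is reviewed.

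In SAP 2.2, replace the catch-all with deviation types fixed before the review, and state how infusion interruptions and rate changes are classed for PP purposes.

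The cost is SAP wording, one extra listing and a change in the order of the meeting; data collection is unaffected. The protection is not complete. EULAR response is calculated at every visit after baseline (protocol 8.3) and bears on access to other RA medication from week 2 (protocol 5.2.4), so investigators at the review may already know some outcomes.

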4.1 General Statistical Considerations

Individual data listings will be provided for all subjects enrolled, sorted by treatment group, site, subject and time point. Summary tables will be presented for the safety population by treatment group.

Descriptive statistics for continuous variables will be number of subjects (N), mean (Mean), standard deviation (SD), median (Median), minimum (Min) and maximum (Max). For categorical variables, the absolute (N) and relative frequency

(%) will be tabulated. Confidence intervals (CI) for mean values will be added if appropriate.

The analyses of the primary and key secondary efficacy endpoint are described in sections 4.8.1 and 4.8.2.

Due to early termination of the study, the sample size will be much less than planned. As a result, the statistical power can be inadequate for the planned gatekeeping methodology. Therefore, standard hypothesis testing methods may be used instead to analyze the data.

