4.8 Efficacy Analysis

The primary and key secondary analyses will be completed for the ITT and PP populations.

Due to early termination of the study, the sample size will be much less than planned. As a result, the statistical power can be inadequate for the planned gatekeeping methodology. Therefore, standard hypothesis testing methods may be used instead to analyze the data.

[figure not shown]
To account for these possibilities and to facilitate better understanding of the data, the data will be analyzed 'as planned' in the protocol AND using more simple, unadjusted alpha analyses with basic chi-square tests. Therefore the data (Table 8A and 8B) will be analyzed two ways:

- Original Primary and Key Secondary Analyses using Hochberg's procedure and gatekeeping methods
- Modified Primary and Key Secondary Analyses using simple chi-square tests.

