4.8.2 Simplified Analyses

The primary and key secondary analyses will be completed using the Hochberg and gatekeeping methodology described above but will also be analyzed using simple chi-square tests.

The simplified analyses will be completed for the ITT and PP populations.

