4.11 Modifications from the statistical section in the protocol

The protocol stated hypotheses with one-sided testing using less than and greater than symbols. This is corrected in the SAP to two-sided hypotheses, as planned, using equal and not equal symbols.

The protocol stated that Cochrane-Mantel-Haenszel test stratified by study site will be used for the primary analysis. However, this conflicts with the primary and key secondary hypotheses planned in the protocol which are not stratified, so this is revised in the SAP to match with the planned hypotheses.

Due to early termination of the study, the sample size will be much less than planned. As a result, the statistical power can be inadequate for the planned

gatekeeping methodology. Therefore, standard hypothesis testing methods may be used instead to analyze the data (see section 4.8).

5. Interim analyses

No interim analyses were planned.

6. Sample size and Power calculations

A total of 330 subjects were to be enrolled and randomized into 3 groups (1:1:1).

The EULAR response rate will be considered as primary parameter. See Appendix B for details on scoring and coding. There is a special interest in the percentage of subjects with an EULAR response category of good or moderate (good and moderate combined) and the percentage of subjects with an EULAR response category of only good. These subjects will be called EULAR responders and EULAR good-responders, respectively.

[figure not shown]

Primary endpoint:

- The percentage of EULAR responders (good + moderate) at Day 8

Key secondary endpoints:

- The percentage of EULAR good responders at Day 8
- The percentage of EULAR responders at Day 15
- The percentage of EULAR good responders at Day 15

[REDACTED]

[REDACTED]
[REDACTED]
[REDACTED]
[REDACTED]
[REDACTED]
[REDACTED]

The sample size calculation is based on estimates from [REDACTED]

[REDACTED]
[REDACTED]
[REDACTED]
[REDACTED]
[REDACTED]
[REDACTED]
[REDACTED]
[REDACTED]
[REDACTED].

Although the above described the planned sample size, the study enrollment did not reach the planned goal, and the study may likely have inadequate statistical power.

7. Tables, Listings and Figures

Below are the titles for the planned study tables, listings and figures

Table 1	Subject Distribution
Table 2.A	Subject Distribution By Center (ITT)
Table 2.B	Subject Distribution By Center (PP)
Table 3.A	Demographics and Baseline Characteristics (ITT)
Table 3.B	Demographics and Baseline Characteristics (PP)

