Table 4	Medical and Surgical History (ITT)
Table 5.A	Dose Administration (ITT)
Table 5.B	Dose Administration (PP)
Table 6.A	Dose Administration by Visit (ITT)
Table 6.B	Dose Administration by Visit (PP)
Table 7.A	Dose Administration by Center (ITT)
Table 7.B	Dose Administration by Center (PP)
Table 8.A	EULAR Good/Moderate Responders - Original and Simplified Analyses (ITT)
Table 8.B	EULAR Good/Moderate Responders - Original and Simplified Analyses (PP)
Table 9.A	EULAR Response by Visit (ITT)
Table 9.B	EULAR Response by Visit (PP)
Table 10.A	Time to First EULAR Good/Moderate Response (ITT)
Table 10.B	Time to First EULAR Good/Moderate Response (PP)
Table 11.A	DAS28 Scores (ITT)
Table 11.B	DAS28 Scores (PP)
Table 12.A	Tender and Swollen Joints (ITT)
Table 12.B	Tender and Swollen Joints (PP)
Table 13.1.A	Visual Analog Scale (VAS) – Patient Pain (ITT)
Table 13.1.B	Visual Analog Scale (VAS) – Patient Pain (PP)
Table 13.2.A	Visual Analog Scale (VAS) – Patient RA Disease Activity (ITT)
Table 13.2.B	Visual Analog Scale (VAS) – Patient RA Disease Activity (PP)
Table 13.3.A	Visual Analog Scale (VAS) – Investigator RA Disease Activity (ITT)
Table 13.3.B	Visual Analog Scale (VAS) – Investigator RA Disease Activity (PP)
Table 14.A	American College of Rheumatology (ACR) 20/50/70 Response (ITT)
Table 14.B	American College of Rheumatology (ACR) 20/50/70 Response (PP)
Table 15.1.A	SF-36 Physical Component Score (ITT)
Table 15.1.B	SF-36 Physical Component Score (PP)
Table 15.2.A	SF-36 Mental Component Score (ITT)

Table 15.2.B	SF-36 Mental Component Score (PP)
Table 16.A	Health Assessment Questionnaire (HAQ) (ITT)
Table 16.B	Health Assessment Questionnaire (HAQ) (PP)
Table 17.A	Functional Assessment of Chronic Illness Therapy (FACIT) Fatigue Score (ITT)
Table 17.B	Functional Assessment of Chronic Illness Therapy (FACIT) Fatigue Score (PP)
Table 18	Maintenance Improvement at Week 12 (Day 85)
Table 19.A	Health Economics Questionnaire (HEQ) at Week (Day 85) (ITT)
Table 19.B	Health Economics Questionnaire (HEQ) at Week (Day 85) (PP)
Table 20.A	Laboratory Results (SAF)
Table 20.B	Laboratory Abnormalities (SAF)
Table 20.C	Laboratory Shift (SAF)
Table 21	Vital Signs (SAF)
Table 22	Physical Exam (SAF)
Table 23	12-Lead ECG (SAF)
Table 24.A	Concomitant Medications Summary (SAF)
Table 24.B	Concomitant Medications (SAF)
Table 25.A	Adverse Event Summary (SAF)
Table 25.B	Adverse Events
Listing 1	Subject Disposition

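### For the four EULAR responder endpoints the SAP plans tests of the arms but no effect estimate or confidence interval, and it drops the protocol's odds-ratio model without listing this

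*Combined protocol and SAP*

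**What the plan says.** SAP 4.8 sets out two analyses of the primary and key secondary endpoints: "Original Primary and Key Secondary Analyses using Hochberg's procedure and gatekeeping methods" and "Modified Primary and Key Secondary Analyses using simple chi-square tests". SAP 4.8.1 gives the hypotheses and the alpha allocation. The difference in rates appears there only inside the null and alternative hypotheses. SAP 4.8.2 adds that the same endpoints follow the gatekeeping method "but will also be analyzed using simple chi-square tests". Neither section asks for a rate difference, risk ratio, odds ratio or interval. The titles of Tables 8.A and 8.B in SAP 7 name only the original and simplified analyses.

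SAP 4.1 covers description. Counts and percentages are tabulated ("For categorical variables, the absolute (N) and relative frequency"), and for intervals it says "Confidence intervals (CI) for mean values will be added if appropriate".

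SAP 4.1, 4.8 and 4.11 state that early termination leaves a sample much smaller than planned. SAP 6 concludes that "the study may likely have inadequate statistical power".

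The protocol planned more. Section 10.2 has a logistic regression of the primary endpoint with study site and baseline covariates, presents odds ratios, and leaves the choice of further covariates to the SAP. Section 10.3 analyses the key secondary endpoints in the same way as the primary. The SAP contains no such model and names no covariates for it. SAP 4.11 lists three changes (two-sided hypotheses, removal of the stratified test, and simpler tests because of early termination), and this is not among them.

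**The concern.** When power is low, a non-significant result is likely even if a useful difference exists. A p-value above 0.05 then fits both no difference and a large one. What separates these is the estimated difference and the range of values the data do not exclude.

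The SAP foresees low power, but its response is a second, less strict set of tests. That does not help with imprecision. At stake is what can be concluded from the main comparison of a stopped trial, and whether the effect measure and interval method are fixed before unblinding.

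The dropped logistic model adds a documentation gap. It was the only between-arm effect measure in the protocol for these endpoints. SAP 4 undertakes to identify and document differences from the protocol, and SAP 4.8 says the data will be analysed as planned in the protocol.

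**Working it through.** **Plan's own figure.** Protocol 4.4 gives 110 per arm, 330 in total, with about 10% drop-out. 3 × 110 = 330, and 110 × 0.90 = 99 evaluable per arm. The design power cannot be reproduced: the assumed rates are not given in protocol 4.4 and are blacked out in SAP 6.

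**Assumptions.** The achieved number per arm and the response rates are not in the documents. The inputs below (99, 50 or 30 per arm; rates of 40%, 60% and 75%) are illustrations.

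**Precision.** The approximate 95% half-width for a difference of two rates, with rate p in both arms and n per arm, is 1.96 × √(2p(1 − p)/n). With p = 0.60:

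- n = 99: 1.96 × √(0.48/99) = 13.6 points
- n = 50: 1.96 × √(0.48/50) = 19.2 points
- n = 30: 1.96 × √(0.48/30) = 24.8 points

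**Power.** Two-proportion formula, two-sided 0.05, one comparison, no multiplicity adjustment:

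| n per arm | 60% vs 75% | 40% vs 60% |
|---|---|---|
| 99 | 62% | 81% |
| 50 | 36% | 52% |
| 30 | 23% | 34% |

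**What the interval adds.** Take 18/30 versus 12/30. The pooled rate is 0.5, so z = 0.20/√(0.25 × 2/30) = 1.55 and the chi-square p is 0.12. The Wilson limits are 0.423 to 0.754 and 0.246 to 0.577. Newcombe's limits for the difference are:

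- lower: 0.20 − √[(0.600 − 0.423)² + (0.577 − 0.400)²] = −0.05
- upper: 0.20 + √[(0.754 − 0.600)² + (0.400 − 0.246)²] = +0.42

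Now take 15/30 versus 15/30: p = 1.0, difference 0, Newcombe interval −24 to +24 points. Both results are non-significant. The first has a point estimate of +20 points and leaves up to +42 open; the second is centred on zero and still does not exclude 20 points either way.

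**Baseline adjustment.** Good response requires DAS28 of 3.2 or less, so it may depend on baseline DAS28. Simulations of a logistic model standardised over baseline assumed a baseline mean of 4.8, SD 0.9, and a change SD of 1.0. If change is independent of baseline, the variance of the good-response difference falls by about 9–11%. If improvement rises by 0.2 per unit of baseline DAS28, the fall is about 4–8%; at 0.4 it is about zero. For good-plus-moderate response the adjusted-to-unadjusted ratio is 0.99–1.02. Even an 11% cut narrows an interval by only 1 − √0.89 ≈ 6%.

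**The case against.** Several points on the other side stand.

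- A reader might infer that nothing but p-values will be reported. That is too strong. Each arm's count and percentage are tabulated under SAP 4.1, so a crude difference and interval can be derived. SAP 4.8.3 also plans ANCOVA of DAS28, the score underlying EULAR response, at Weeks 1 and 2 if the scores look approximately normal.
- A reader might infer that the trial cannot answer its own question, or that the SAP will treat a non-significant result as no difference. The documents do not support either. No passage states such a reading, and the SAP repeatedly warns of low power.
- The SAP 4.1 sentence on intervals for means sits in a paragraph on descriptive statistics, and the next paragraph refers the reader to 4.8.1 and 4.8.2. It does not forbid intervals for rates. The point rests on their absence from 4.8.
- SAP 7 gives table titles only. The layouts of Tables 8.A and 8.B are not in the documents and may show a difference with an interval.
- A reader might infer that adjustment for baseline DAS28 is needed. Unadjusted comparison under randomisation is valid, the gain may be nil, and a logistic model may be unstable if good responses are few.

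These points limit the finding. They do not supply a pre-specified effect measure, an interval method, or a record of why the protocol's model was dropped.

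**Conclusion.** The point holds as a gap in the planned between-arm comparison. For the four responder endpoints and two dose comparisons (eight contrasts), the SAP's text specifies tests without an estimate or interval, in the situation where it expects power to be inadequate. The protocol's odds-ratio model is absent from the SAP and from its list of changes. The planned tests are not invalidated by this, and no data are lost.

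The size depends on an unknown sample. At an assumed 60% rate, the uncertainty left unreported is about ±14 points with 99 per arm, ±19 with 50 and ±25 with 30. Baseline adjustment is worth about 0–11% of variance for good response, depending on the assumed relation between baseline and change, and is negligible for good-plus-moderate response. It is supportive only. The change is worth making because it costs little and affects what an underpowered result can say.

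**What to change.** In SAP 4.8.1, 4.8.2 and Tables 8.A and 8.B, report the difference in responder rates with a 95% confidence interval (Newcombe or Miettinen-Nurminen, chosen before unblinding). Do this for each Nanocort dose versus Depo-Medrol and for each of the four endpoints. State that interpretation will rest on the interval.

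Restore the logistic sensitivity analysis of protocol 10.2 and 10.3 with baseline DAS28 as a named covariate, labelled supportive, or list its removal with a reason in SAP 4.11.

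The cost is a few table columns, one model the protocol already planned, and a sentence on interpretation. No new data are needed and the tests do not change.
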